6.2.2 Secondary objective (Detection of significant cancer)

The detection of significant cancers will be analysed in the same way as the detection of insignificant cancers except that no hypothesis testing will be performed.

6.2.3 Endpoint Definitions

Several different definitions of significant and insignificant cancer will be considered, see Table below. The main result and conclusion of the study results will be based upon the first definition of significant (Gleason score >6) versus insignificant cancer (Gleason=6) based on findings in core biopsies. Clinically significant cancer is for the first definition defined as not fulfilling the criteria for clinically insignificant cancer but we also added two definitions used in the PROMIS study. The different definitions of clinically insignificant cancer will be based on pathology evaluation in core biopsies, see section 5.1, and in prostatectomy specimen, when available. The pathology evaluation includes Gleason score and tumor size.

Endpoint definitions

Definition of insignificant cancer	Gleason biopsy	Cancer involvement in biopsies	Prostatectomy outcome	Comments
First definition	GS=6	Any	Any	
Second definition	GS=6	Maximum 2 sectors involved, T1c, PSAD<0.15 and unilateral involvement	Any	
Third definition	GS=6	Maximum 2 sectors involved, T1c, PSAD<0.15 and unilateral involvement	GS=6, no EPE Tumor volume < 0.5 cc	Biopsy criteria only to use if no prostatectomy is performed
Fourth definition	GS≤7	Maximum 2 sectors involved, T1c, PSAD<0.15 and unilateral involvement	GS≤7, no EPE Tumor volume < 0.5 cc	Biopsy criteria only to use if no prostatectomy is performed
Definition of significant cancer				
First definition	GS>6	any	Any	
Second definition	GS>3+4	A maximum core cancer length of ≥ 6 mm	Any	Gleason Biopsy and/or cancer involvement
Third definition	GS>3+3	A maximum core cancer length of ≥ 4 mm	Any	Gleason Biopsy and/or cancer involvement

Another endpoint in this study is primary treatment split into i) treated with radical prostatectomy ii) treated by radical radiation therapy iii) hormonal therapy iiiii) surveillance and iiiiii) other treatments. No significance testing will be performed.

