4 STUDY INTERVENTION

4.1 Intervention

Arm (1) (reference arm)

- Screen-negative: If the total-PSA level is “normal”, i.e. below the cut-off 3.0 ng/mL, no further testing or examination will be performed, but all men will be re-invited.
- Screen-positive: If the total-PSA level is “elevated” above the cut-off i.e. ≥ 3.0 ng/mL, the man will be invited for an MRI.

All men will be recommended standard biopsy, i.e., digital rectal exam followed by TRUS-guided 12-core standard prostate biopsy according to the screening protocol. These standard biopsies will be taken with both the urologist and subject blinded to the MRI result. After these standard biopsies, the study nurse will show the urologist the result from the MRI examination, and in case of suspicious lesion at MRI, 3-4 targeted* biopsies in each of these lesions will be performed in the same séance; 3 targeted biopsies if one of the systematic biopsies already hit the area, and 4 targeted biopsies if otherwise.

- Men in whom MRI for any reason is not achievable or the result is inconclusive will only undergo systematic biopsies

Arm (2) (first experimental arm)

- Screen-negative: If the total-PSA level is “normal”, i.e., below 3.0 ng/mL, no further testing or examination will be performed. The man will be re-invited for screening identical to Arm (1).
- Screen-positive: If the total-PSA level is “elevated” ≥ 3.0 ng/mL, he will be offered MRI.
 - If the MRI is positive (PI-RADS 3-4), only targeted* biopsies will be performed, i.e. 4 biopsy cores targeted against each suspicious lesion, but no systematic biopsies.
 - If the MRI is positive (PI-RADS 5), targeted* biopsies will be performed, i.e., 4 biopsy cores targeted against each suspicious lesion but also systematic biopsies. Changed 2018-10-15 (see amendment 5)
 - If the MRI is negative no biopsies will be performed.
 - If the MRI is negative and PSA ≥ 10 and PSA density (PSAD), ≥ 0.1 , systematic 12-core biopsies will be performed. PSA cut off changed 2016-03-01 from 20 to 10 ng/mL (see amendment 1).
 - Men in whom MRI for any reason is not achievable, or the MRI is technically inferior (for example in men with hip prosthesis), are invited for urological examination with digital rectal examination (DRE) and transrectal ultrasound

(TRUS). These men are included in the intention to screen analysis but not in the per protocol analysis (see 6.2.1).

Arm (3) (experimental arm II)

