- Identical to arm (2) except that the PSA-cut off is lower, ≥ 1.8 ng/mL.

Men in Arm 2 and 3 with cancer diagnosed at targeted biopsies during screening round 1 are recommended completion with systematic biopsies 6-12 weeks after the first biopsy.

* Targeted biopsy = biopsy targeted against MRI positive areas (suspicious for cancer)

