6.2 Analysis plan for the primary and secondary endpoints

6.2.1 Primary objective (Detection of insignificant cancer)

- Hypothesis

The proportion of men with insignificant cancer detected by PSA testing with threshold 3 ng/mL, systematic biopsies and MRI-targeted biopsies (p_1) will be different from the proportion detected when omitting systematic biopsies (p_2):

H_0 (null hypothesis): $p_1 = p_2$

H_A (alternative hypothesis): $p_1 \neq p_2$

Although the hypothesis of the investigators is one-sided, that MRI-targeted biopsies only will lower the proportion, the test is two-sided to allow for a significant effect in both directions.

- Analysis populations

First assessment (after completion of screening round 1): All men in arm 1 will be compared to all men in arm 2 and 3 combined. However, for men in arm 3, cancers detected in men with PSA < 3 ng/mL will be ignored.

Later assessments: the analysis will compare all men in arm 1 with all men in arm 2.

The analyses will primarily be carried out according to the intention to treat (ITT) principle, which here means that all men will be included in the analysis and belong to the arm they were allocated to, irrespective of whether they completed the intended diagnostic pathway with MRI and biopsies or not.

Furthermore, per protocol analyses will be carried out including only men who strictly follow the protocol.

An additional analyses will compare men in arm 1 who underwent MRI followed by systematic and possible targeted biopsies (if MRI positive) with those in arm 2 and 3 who underwent MRI and also targeted biopsies but ignoring results from possible systematic biopsies if those were taken at the primary biopsy and the targeted biopsies were benign.

- Analysis

Outcome measure is the relative difference of the proportion of insignificant cancers detected in arms 2 and 3 combined vs arm 1 (the cancers detected in men with PSA below 3 ng/mL in arm 3 will be ignored). In later assessments only arm 1 and 2 will be included. The result will be presented as a point estimate with a two-sided 95% confidence interval, and a p-value of the hypothesis test. Significance testing will only be carried out for the first definition of insignificant cancer (Gleason grade 3+3). The score method will be used for testing and confidence intervals (27). A p-value below 5% will be considered statistically significant.

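### After round 1, the sector and laterality limits in definitions 2 to 4 of insignificant cancer rest on fewer sampled sectors in arm 2 than in arm 1

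*Protocol*

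**What the plan says.** Section 6.2.3 lists four definitions of insignificant cancer. The first is biopsy Gleason 6 with no other condition. The second to fourth add "Maximum 2 sectors involved, T1c, PSAD<0.15 and unilateral involvement". For the third and fourth a comment limits this: "Biopsy criteria only to use if no prostatectomy is performed".

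The biopsy procedures are in section 4.1:

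- **Arm 1.** Every man with PSA at or above 3 is recommended "digital rectal exam followed by TRUS-guided 12-core standard prostate biopsy according to the screening protocol". On masking: "These standard biopsies will be taken with both the urologist and subject blinded to the MRI result". The MRI is then disclosed, and suspicious lesions receive 3-4 further cores.
- **Arms 2 and 3, PI-RADS 3-4.** "only targeted* biopsies will be performed, i.e. 4 biopsy cores targeted against each suspicious lesion, but no systematic biopsies".
- **Completion.** "Men in Arm 2 and 3 with cancer diagnosed at targeted biopsies during screening round 1 are recommended completion with systematic biopsies". The interval stated is 6 to 12 weeks from the initial procedure.

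Section 5.1 gives compensation for sampling error as the purpose of the completion cores, and counts them if taken within one year of the diagnostic biopsy. Its reference biopsy table lists 12 additional cores for MRI-positive men in arms 2 and 3 whose targeted cores show cancer. A triple-asterisk footnote repeats this. Neither the table cell nor that footnote names a screening round.

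Sections 2.5 and 6.2.1 compare arm 1 with arms 2 and 3 combined after round 1. Later assessments compare arm 1 with arm 2 over all screening visits up to 30 June 2022, and again 2, 6 and 10 years after that.

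**The concern.** The number of involved sectors, and whether both sides are involved, can only be counted where cores were taken. If one arm samples 12 posterior sectors plus the lesion and the other samples the lesion alone, the same cancer can fail the limit in the first arm and pass it in the second. The between-arm ratio under definitions 2 to 4 then mixes a real change in overdiagnosis with a difference in how the endpoint is measured.

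A smaller, separate question concerns T1c. It is a clinical stage, and in ordinary usage it turns on what the examining finger feels. Who examines, and with what knowledge of the MRI, could therefore affect it.

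**Working it through.** **1. The plan's own figure.** Section 6.1 assumes 9% insignificant cancer in arm 1 and a 50% reduction, so 4.5% in arms 2 and 3 and a ratio of 0.50. The settings are 80% power, two-sided 5%, and 1:2 allocation for arm 1 against arms 2+3. With p̄ = (0.09 + 2 × 0.045)/3 = 0.06, the pooled formula is

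n₁ = [1.96 √(0.06 × 0.94 × 1.5) + 0.842 √(0.09 × 0.91 + 0.045 × 0.955/2)]² / 0.045² ≈ 350.

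The continuity correction raises this to 382, or 3 × 382 = 1,146 in all, which is 1.5% below the stated 1,164. The figure reproduces. The added sector and stage conditions do not enter it, so the present point does not touch it.

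**2. What the sector and laterality limits rest on, by group.**

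| Men with an MRI lesion and cancer | Round 1 | Later rounds |
|---|---|---|
| Arm 1 | 12 systematic + lesion cores | 12 systematic + lesion cores |
| Arm 2, PI-RADS 3-4, PSA <10 or PSAD <0.1 | Lesion cores, then recommended completion cores | Lesion cores only under 4.1; lesion plus 12 completion cores as the 5.1 table reads |
| Arm 2, PI-RADS 5 | Same route in the 5.1 table, whose footnote excludes round 1 from the added cores | 12 systematic + lesion cores (rule dated 15 October 2018) |
| Arm 2, PSA ≥10 and PSAD ≥0.1 | 12 systematic + lesion cores | 12 systematic + lesion cores |

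The second row, later rounds, is where the arms part and where the protocol gives two answers. The 5.1 table does mark a round restriction elsewhere, in its PI-RADS 5 footnote, so its silence on completion cores cannot simply be read as meaning round 1.

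**3. Direction.** For a given man with his Gleason score held fixed, the sectors found positive on lesion cores are a subset of those found positive on lesion plus systematic cores. Anyone who passes the limits with more cores also passes with fewer. Measurement alone can therefore only raise the share classed as insignificant in arm 2.

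**4. Size, for illustration only.** Let q₁ and q₂ be the shares of Gleason 6 cancers that meet the added conditions under arm 1 and arm 2 sampling. Then

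ratio under definition 2 = ratio under definition 1 × q₂/q₁.

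Take the planned 0.50 and assume q₁ = 0.6:

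- q₂ = 0.6: 0.50 × 0.6/0.6 = 0.50
- q₂ = 0.7: 0.50 × 0.7/0.6 = 0.58
- q₂ = 0.8: 0.50 × 0.8/0.6 = 0.67
- q₂ = 0.9: 0.50 × 0.9/0.6 = 0.75

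Later assessments pool round 1 with later rounds, and only some arm 2 men are judged on lesion cores. If those men pass at 0.9 and all others at 0.6, then q₂ = 0.7 corresponds to (0.7 − 0.6)/(0.9 − 0.6) = one third judged on lesion cores, and q₂ = 0.8 to two thirds. The documents give none of these shares. Observed q₂/q₁ would also carry genuine case mix, since arm 1 includes MRI-negative cancers found by systematic cores. Only the measurement part has a known direction.

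**5. T1c.** In arm 1 the rectal examination comes before the systematic cores, and the MRI is shown after them. For arms 2 and 3, section 4.1 names a rectal examination only for men without a usable MRI. For MRI-positive men the source of T1c and any masking are not described.

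**The case against.** The strongest reply is that the protocol saw the problem and dealt with it. For round 1 this largely stands: completion cores are recommended, counted, and justified as compensation for sampling. A reader might infer from the arm descriptions that arms 2 and 3 never sample 12 sectors. The documents do not support that for the first assessment. What remains in round 1 is that completion is only recommended, and that cores taken later than one year do not count.

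A reader might also infer that, after round 1, an arm 2 man meets the limits almost by construction. That goes too far. PI-RADS 5 men under the 2018 rule, and men with PSA ≥10 and PSAD ≥0.1, have systematic cores. Up to three lesions can be reported per man, so involvement on both sides or in several sectors can still be found.

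On T1c, it is tempting to say that knowing the lesion pushes the examiner toward T2 and so favours arms 2 and 3. This is conjecture from the protocol's silence. How stage is derived may also be set out in an analysis plan that is not shown.

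Finally, the consequence is limited. Section 6.2.3 states: "The main result and conclusion of the study results will be based upon the first definition of significant" versus insignificant cancer, and section 6.2.1 confines testing to the first definition of insignificant cancer. The protocol does not call the other definitions robustness checks. This stands and sets the weight of the point. It does not remove it, because 6.2.3 says the further definitions will be considered and does not confine them to round 1.

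**Conclusion.** The point holds for the later arm 1 versus arm 2 assessments. Under section 4.1, arm 2 men with PI-RADS 3-4 lesions and PSA <10 or PSAD <0.1 are held to sector and laterality limits on lesion cores alone, while arm 1 men have 12 systematic cores as well. The measurement effect can inflate insignificant cancer in arm 2 and so understate the benefit under definitions 2 to 4. Its size is unknown, and the range 0.58-0.75 in place of 0.50 rests wholly on assumed shares.

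The conclusion assumes that section 4.1 governs later rounds. If the 5.1 table governs, sampling in later rounds is equalised as in round 1, and what remains is the contradiction between the two sections. In definitions 3 and 4 the effect reaches only men without prostatectomy.

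That T1c may be obtained differently by arm is a lesser point, with no established direction. Neither issue bears on the sample size or the test of the first definition. This is a correction worth making to supplementary estimates, not a threat to the main result.

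**What to change.** 1. **Reconcile section 4.1 with the reference biopsy table and its triple-asterisk footnote in 5.1**, so that the set of biopsies counted in later rounds has one reading. Which of the two is clinically intended is for the investigators to state.
2. **In 6.2.3, add a reduced version for the later assessments.** Give between-arm estimates under definitions 2 to 4 also without the sector, laterality and T1c conditions, which leaves biopsy Gleason and PSAD <0.15 for men without prostatectomy. Note that biopsy Gleason itself depends on which cores are taken, so this reduces the artefact and does not abolish it. For round 1, also show definitions 2 to 4 by whether completion biopsies were done.
3. **For the remaining rounds, where a rectal examination is done, record T stage before lesion location is shown.** This cannot repair round 1, which section 9.3.1 describes as completed in 2021. Nor can it hide that an arm 2 or 3 man attending for targeted biopsy is MRI-positive.

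The cost is one or two supplementary tables and one line in the visit procedure, with no change to sample size. The drawback is that the reduced version is less specific for small cancers. This matters most for definition 4, where any cancer of Gleason 7 or below with PSAD <0.15 would count as insignificant whatever its extent, so the reduced version should stand beside the full definition and not replace it.

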6.3 Substudies

For the substudies separate analysis plans will be written prior to any analysis.

6.4 Statistical software

The statistical analysis will be performed using R Statistical Software, version $\geq 4.0.4$ (Foundation for Statistical Computing, Vienna, Austria).

7 TRIAL MANAGEMENT

7.1 Study secretariat

We will use the same structural organization as in a previous study (Göteborg-1). With 25 years of prior experience from running a 20,000-men screening trial (Göteborg-1), it is expected that this trial can be carried out utilizing the same organization and a fully equipped screening center. The infrastructure for performing this study already exists. We will use the same processes (except for MRI) as in the Göteborg-1 trial.

7.2 Advisory board

An advisory board with 4-5 members will meet with the study board when needed. This committee will advise the study board in recommending possible extensions of the study and changes/amendments in the protocol. The Advisory board will also be asked for advise in other questions brought up by the study board. The Advisory board will be recruited from national and international experts in the field. For participants, see Appendix 2.

8 DATA COLLECTION AND MONITORING AND ADVERSE EVENT REPORTING

8.1 Database

The study database will be kept at a server at University of Gothenburg for 35 years.

8.2 Monitoring

Data will be prospectively and continuously recorded in the screening database. Several quality data checks will be performed.

8.3 Adverse Event Reporting

Adverse events (see toxicity) from MRI and TRUS biopsy will be recorded continuously and summarized once a year. This summary will be discussed within the study board and possibly together with the Advisory board. The study protocol follows principally clinical recommendations from the Swedish Board of Health and Welfare. One critical point in this study is a potential risk to delay diagnosis of serious cancer when omitting biopsy in men with a negative MRI (and a PSA < 10) in Arm 2 and 3. Therefore, analysis of the incidence of interval cancers in these men is planned as well as studying the characteristics of cancers detected at follow-up screens in men with elevated PSA and negative MRI in previous screening rounds. These data will be presented to the Advisory Board for recommendations. No other stopping rules are specified within the protocol.

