4.4 Special circumstances

Due to high risk of potentially lethal prostate cancer, all men with PSA ≥ 10.0 ng/mL, irrespective of Study Arm, will, for ethical reasons, be recommended 12 standard TRUS-biopsies plus additional targeted biopsies if positive MRI. Exceptions are those with PSAD < 0.1.

On March 1, 2016, the PSA level indicating high risk of lethal prostate cancer was adjusted from ≥ 20.0 ng/mL to PSA ≥ 10.0 ng/mL in order to harmonize with National standardized course of medical care (SVF) for prostate cancer.

Since October 15, 2018, all men with MRI showing a PI-RADS-score 5 in Arm 2 and Arm 3, should, apart from the targeted biopsies, also undergo systematic biopsies with 12 cores. All men with PI-RADS 5 lesions and negative biopsies should be re-evaluated at a radiology conference (round) and, if no adjustment of PI-RADS score, a new set of targeted biopsies should be carried out within 3 months.

The study design is depicted in Figure 1.

5 Study organisation and infrastructure

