5.1 Outcome Ascertainment

The project is planned to run for an initial 4 years with an evaluation of the primary and some of the secondary objectives during year 4. Details of outcomes and times of assessments are given in Table 1 (p 19)

Prostate cancer diagnosis

Reporting of cancer to the National Prostate Cancer Register and the National Cancer Register is mandatory by Swedish law. All diagnoses made in the study will be continuously recorded in the study database. Every 3 months, cross-linkage on the study participants' personal identification number will also be performed with the study database and the cancer registries, to ensure accuracy and completeness of the diagnoses.

Prostate biopsies

One internal pathologist with 25 years of experience of prostate pathology will review the prostate biopsies in the study. To minimize heterogeneity in Gleason grading between different pathologists a secondary review of biopsies with a cancer diagnosis will be conducted by two external pathologists. The reviewers are blinded to the primary local assessment and work independently from each other. Each core harbouring cancer is reviewed separately. The final Gleason score for each patient is based upon these three verdicts. In case of agreement between at least two of the reviewers the Gleason score is set. In case all three reviewers differ from each other the "middle" assessment will be used. In the first screening round the internal pathologist is [name] with 25 years of experience of prostate pathology, and the external pathologists are [name] at Karolinska Institute, Stockholm and [name] at University of Oslo.

Reference for biopsy outcome

For analysing the endpoints based on prostate biopsies, different sets of biopsies will be taken into account (see table below). Adding systematic biopsies at a second occasion in men with cancer detected with targeted biopsies in arms 2 and 3 is an attempt to compensate for possible sampling errors due to the fact that MR positive and MR negative cancers were primarily biopsied with two different techniques. Only systematic biopsies taken within one year after the diagnostic biopsy are taken into account (arms 2 and 3).

If MRI, for any reason, is not achievable or inconclusive, see 4.1

Additional biopsies taken after what here is stated are not considered

Arm 1	Arm, 1	Arm 2 and 3 (PSA < 10 ng/mL or PSA ≥ 10 and PSAD < 0.1)		Arm 2 and 3 (PSA ≥10 ng/mL and PSAD ≥0.1)	

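### The interval-cancer analysis in section 8.3 is defined for MRI-negative men with PSA below 10, but the protocol also leaves some MRI-negative men with PSA of 10 or more unbiopsied

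*Protocol*

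**What the plan says.** Section 8.3 names the critical safety question as a possible delay in diagnosing serious cancer "when omitting biopsy in men with a negative MRI (and a PSA < 10) in Arm 2 and 3". Two analyses follow in one sentence. For the first, "analysis of the incidence of interval cancers in these men is planned". The second is "studying the characteristics of cancers detected at follow-up screens in men with elevated PSA and negative MRI in previous screening rounds". The results of both go to the Advisory Board for recommendations, and 8.3 states that the protocol contains no other stopping rules.

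The no-biopsy rule itself is set out in three other places.

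- Section 4.1, arm 2: "If the MRI is negative no biopsies will be performed". The exception is "If the MRI is negative and PSA ≥ 10 and PSA density (PSAD), ≥ 0.1 , systematic 12-core biopsies will be performed". Arm 3 is the same apart from its lower PSA cut-off.
- Section 4.4 recommends systematic biopsy at PSA of 10 or more in every arm, then adds: "Exceptions are those with PSAD < 0.1".
- The biopsy reference table in section 5.1 has a column headed "Arm 2 and 3 (PSA < 10 ng/mL or PSA ≥ 10 and PSAD < 0.1"; its cell for MRI-negative men specifies no biopsy.

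Section 4.1 also records the history of the threshold: "PSA cut off changed 2016-03-01 from 20 to 10 ng/mL".

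**The concern.** The interval-cancer analysis exists to show whether skipping biopsy after a negative MRI lets serious cancers surface clinically between screens. Its population should therefore be the men in whom biopsy was skipped. Section 8.3 uses PSA below 10 alone, whereas the rule elsewhere uses PSA and PSAD together, and it used a different PSA value before March 2016. An analyst who follows 8.3 as written would drop the unbiopsied men with the highest PSA from the interval-cancer count.

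The second analysis does not fill that gap, because it concerns cancers found at a later screen. Section 4.2 sets re-invitation at 2 years for PSA of 1.2 or more, and at 4 years after a negative MRI and/or biopsy twice in a row. A cancer diagnosed clinically in that window, or in a man who does not return, can appear only in the first analysis. What is at stake is the completeness of the evidence on which the Advisory Board is asked to advise. No primary or secondary endpoint is affected.

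**Working it through.** The plan states no figure for this group, so the check compares the men left unbiopsied with the men each analysis covers.

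**Inputs.** The no-biopsy rule comes from sections 4.1 and 4.4 and the table in 5.1. The date and size of the threshold change come from 4.1 and 4.4. The two analysis populations come from 8.3.

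**Step 1: who is unbiopsied by rule.** Biopsy after a negative MRI requires PSA ≥ 10 and PSAD ≥ 0.1 together. A man is therefore unbiopsied if PSA < 10, or if PSA ≥ 10 and PSAD < 0.1. The 5.1 column heading gives the same two-part condition. Before 1 March 2016 the PSA part was ≥ 20, so PSA 10–19.99 did not reach it.

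**Step 2: compare with 8.3, taken literally.**

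| MRI-negative men, arms 2 and 3 | Biopsy under the rule | Interval-cancer analysis | Follow-up-screen analysis |
|---|---|---|---|
| PSA from the arm's cut-off to below 10 | Omitted | Covered | Covered |
| PSA ≥ 10, PSAD < 0.1 | Omitted | Not covered | Covered if they attend |
| PSA 10–19.99, before 1 March 2016 | Below the trigger then in force | Not covered | Covered if they attend |
| PSA ≥ 10, PSAD ≥ 0.1, from 1 March 2016 | Systematic biopsy | Not covered, as intended | Covered if they attend |

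The second and third rows are the mismatch.

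**Step 3: size.** The only base the protocol supplies is its planning assumptions in section 6.1: 36,000 invited, 50% participation, and 7% of participants with PSA ≥ 3. Two of the three arms are concerned:

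36,000 × 0.5 × 2/3 × 0.07 = 840 men with PSA ≥ 3 in arms 2 and 3.

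The protocol gives no distribution of PSA above 10, of MRI result at that level, or of PSAD, so the share of the 840 in row two cannot be computed. Purely as an illustration, assume that 3–8% have PSA ≥ 10, that 40–60% of those are MRI-negative, and that 10–25% of those have PSAD < 0.1:

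- Low: 840 × 0.03 × 0.40 ≈ 10 MRI-negative men with PSA ≥ 10; × 0.10 ≈ 1 man.
- High: 840 × 0.08 × 0.60 ≈ 40 men; × 0.25 ≈ 10 men.

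All three fractions are assumptions. The result indicates a small group and nothing more precise. It does not cover row three, which is a one-time early cohort whose number cannot be approached from the protocol.

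**The case against.** The parenthesis in 8.3 may be shorthand. The sentence concerns omitted biopsy, stands in an adverse-event narrative, and may simply abbreviate the exception by its main criterion. Exact populations may also be fixed in an SAP that is not shown. This is plausible and limits the weight of the point. It does not remove the point, because the abbreviation names a different set of men from the one in 4.1, 4.4 and 5.1.

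A reader might infer that the high-PSA unbiopsied men escape safety review altogether. The protocol does not support that. The second analysis in 8.3 has no upper PSA limit, registry linkage every 3 months (5.1) has no PSA restriction, and section 9.3.1 plans close follow-up of delayed diagnosis without one. The gap lies in the population of one analysis and not in data capture.

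A reader might also infer that leaving these men out makes omitted biopsy look safer than it is, since 4.4 attaches a high risk of lethal cancer to PSA of 10 or more. The same paragraph exempts men with PSAD below 0.1 from the recommendation that it bases on that risk. Nothing in the protocol shows that their interval-cancer rate is higher or lower than in the men who are counted.

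The part about the period before March 2016 rests partly on inference. The protocol says that the PSA cut-off changed. It does not say whether the PSAD condition already applied, or whether men seen earlier were later recalled. That qualification stands.

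**Conclusion.** The point holds in a narrow form. The interval-cancer population stated in 8.3 does not match the protocol's own no-biopsy rule. Followed literally, it leaves out interval cancers in MRI-negative arm 2 and 3 men with PSA of 10 or more and PSAD below 0.1, and in those with PSA 10–19.99 seen while the trigger was 20. Their cancers at later screens remain covered.

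The conclusion about the first group rests on the text alone. The conclusion about the second assumes that the earlier trigger was applied as described. The number of men is probably small and cannot be derived from the protocol, and the direction of any effect on the interval-cancer rate is unknown. The correction is still worth making, because 8.3 itself calls the question critical and these results are what the Advisory Board receives.

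**What to change.** Reconcile 8.3 with 4.1, 4.4 and the 5.1 table. Replace the PSA limit with a definition by what happened: all men in arms 2 and 3 whose biopsy was omitted because of a negative MRI, under the rule in force at the date of their visit. Report men with PSA of 10 or more as a separate line, so that the Advisory Board can see them without their being diluted in the larger group.

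The cost is one sentence in the protocol and one extra line in the report. PSA results already reach the database electronically (3.5), PSAD is needed to apply the existing rule, and diagnoses come through the registry linkage (5.1). If any report has already been made on the narrower population, it would need that line added. The change concerns the analysis population only; the biopsy rule is left as it is.
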